12.5. Appendix 5: Toxicity Management

ANEMIA

Grade 1 (mild) hemoglobin decrease:

Any hemoglobin decrease meeting the definition of Grade 1 must be repeated with the following additional tests:

- peripheral blood smear
- indirect bilirubin (abnormal if increased >50% from baseline)
- haptoglobin (abnormal if ≤ 25 mg/dL)
- reticulocyte count (abnormal if $\geq 4\%$)

If the additional tests are within the normal range, subjects may continue study medication. If one or more of the additional tests is abnormal or suggestive of hemolytic anemia as specified above, subjects will permanently discontinue study medication and be withdrawn from the trial. Subjects should be followed up until resolution of anemia.

Grade 2 (moderate) hemoglobin decrease:

Any hemoglobin decrease meeting the definition of Grade 2 must be repeated with the following additional tests:

- peripheral blood smear
- indirect bilirubin (abnormal if increased > 50% from baseline)
- haptoglobin (abnormal if ≤ 25 mg/dL)
- reticulocyte count (abnormal if $\geq 4\%$)

If the additional tests are within the normal range, subjects may continue study medication. If one or more of the additional tests is abnormal or suggestive of hemolytic anemia as specified above, subjects will permanently discontinue study medication and be withdrawn from the trial. Consultation with a Hematologist should be considered. Subjects should be followed up until resolution of anemia.

Grade 3 (severe) or Grade 4 (potentially life threatening) hemoglobin decrease:

Any hemoglobin decrease meeting the definition of Grade 3 or 4 must be repeated with the following additional tests:

- peripheral blood smear
- indirect bilirubin
- haptoglobin
- reticulocyte count

Subjects will permanently discontinue study medication and be withdrawn from the trial. Consultation with a Hematologist should be considered. Subjects should be followed up until resolution of anemia.

TOTAL BILIRUBIN ELEVATION

Grade 1 (mild) bilirubin elevation (1.1 - 1.5 times ULN) or Grade 2 (moderate - 1.6-2.5 times ULN):

Any bilirubin value above the upper limit of normal must be repeated and fractionated (direct and indirect bilirubin). Subjects may continue study medication. Subjects should be followed up until resolution (return to baseline) of elevation.

Grade 3 (severe – 2.6-5.0 times ULN) or 4 (life-threatening - > 5.0 times ULN) bilirubin elevation:

Any bilirubin value above the upper limit of normal must be repeated and fractionated (direct and indirect bilirubin). Subjects will permanently discontinue study medication and be withdrawn from the trial. Subjects should be followed up until resolution (return to baseline) of bilirubin elevation.

AST AND ALT ELEVATION

See [Appendix 2](#).

RASH

Grade 1 rash (Localized macular rash):

Subjects with Grade 1 rash should be evaluated by the Investigator immediately. A dermatologist may be consulted and a biopsy may be obtained if recommended by the dermatologist. The study drug should be permanently discontinued if the following signs or symptoms are noted at any time:

- Temperature > 38.5°C
- Lymphadenopathy
- Pharyngitis
- Any indication of internal organ involvement (hepatitis, nephritis)

In the absence of the above signs or symptoms, subjects with Grade 1 rash may continue the study drug at the discretion of the Investigator. The subject should be advised to contact the Investigator immediately if there is any worsening of the rash, if any systemic signs or symptoms worsen, or if mucosal ulceration develops. If the rash is considered to be most likely due to concomitant illness or non-study medication, standard management, including discontinuation of the likely causative agent, should be undertaken. If no other causative factor is found after clinical evaluation, the subject may be treated symptomatically until the rash resolves. Antihistamines, topical corticosteroids or antipruritic agents may be prescribed. The subject should remain on the study to be followed for safety and PK as outlined in the Time and Events table.

Grade 2 rash (Diffuse macular, maculopapular, or morbilliform rash OR Target lesions):

Subjects with Grade 2 rash should be evaluated by the Investigator immediately. Digital photographs should be obtained. A dermatologist may be consulted and a biopsy may be obtained if recommended by the dermatologist. The study drug should be permanently discontinued if the following signs or symptoms are noted at any time:

- Temperature > 38.5°C
- Lymphadenopathy
- Pharyngitis
- Any indication of internal organ involvement (hepatitis, nephritis)

In the absence of the above signs or symptoms, subjects with Grade 2 rash may continue the study drug at the discretion of the Investigator. It should be noted that oral mucosal **erosions** may be part of a Grade 2 rash. Any mucosal **ulceration** increases the severity of the rash to at least Grade 3. The subject should be advised to contact the Investigator immediately if there is any worsening of the rash, if any systemic signs or symptoms worsen, or if mucosal ulceration develops. If the rash is considered to be most likely due to concomitant illness or non-study medication, standard management, including discontinuation of the likely causative agent, should be undertaken. If no other causative factor is found after clinical evaluation, the subject may be treated symptomatically until the rash resolves. Antihistamines, topical corticosteroids or antipruritic agents may be prescribed. The subject should remain on the study to be followed for safety and PK as outlined in the Time and Events table.

Grade 3 rash (Diffuse macular, maculopapular, or morbilliform rash with vesicles or limited number of bullae OR Superficial ulcerations of mucous membrane limited to one site):

Subjects with a Grade 3 rash will permanently discontinue the study medication. The subject should be evaluated in the physician's office immediately and should be seen in the physician's office or contacted by phone every 2 days until the rash resolves. A dermatologist should be consulted and digital photographs and a biopsy should be obtained. Antihistamines, topical corticosteroids or antipruritic agents may be prescribed at the discretion of the Investigator. The subject should be advised to contact the Investigator immediately if there is any worsening of the rash, if any systemic signs or symptoms appear, or if mucosal involvement develops. The subject should remain on the study to be followed for safety and PK as outlined in the Time and Events table.

Grade 4 rash (Extensive or generalized bullous lesions OR Stevens-Johnson syndrome OR Ulceration of mucous membrane involving two or more distinct mucosal sites OR Toxic epidermal necrolysis (TEN)):

Subjects with a Grade 4 rash will permanently discontinue the study medication. A dermatologist should be consulted and digital photographs and a biopsy should be obtained. Sponsor and GSK Medical Monitor should be notified of this serious adverse event within 24hr via phone or fax or email. The subject should be closely followed everyday until resolution of the reaction. The subject should remain on the study to be followed for safety and PK as outlined in Time and Events table.

ALLERGIC REACTION

Grade 1 allergic reaction (Pruitis without rash):

Subjects with Grade 1 allergic reaction should be evaluated by the Investigator immediately. The study drug should be permanently discontinued if the following signs or symptoms are noted at any time:

- Temperature > 38.5°C
- Eosinophilia
- Respiratory involvement including bronchospasm, laryngospasm, or angioedema
- Any indication of internal organ involvement (hepatitis, nephritis)

In the absence of the above signs or symptoms, subjects with Grade 1 allergic reaction may continue the study drug at the discretion of the Investigator. The subject should be advised to contact the Investigator immediately if there is any worsening of the allergic reaction and/or if any systemic signs or symptoms worsen. If the allergic reaction is considered to be most likely due to concomitant illness or non-study medication, standard management, including discontinuation of the likely causative agent, should be undertaken. If no other causative factor is found after clinical evaluation, the subject may be treated symptomatically until the rash resolves. Antihistamines, topical corticosteroids or antipruritic agents may be prescribed. The subject should remain on the study to be followed for safety and PK as outlined in the Time and Events table.

Grade 2 allergic reaction (Localized urticaria):

Subjects with Grade 2 allergic reaction should be evaluated by the Investigator immediately. The study drug should be permanently discontinued if the following signs or symptoms are noted at any time:

- Temperature > 38.5°C
- Eosinophilia
- Respiratory involvement including bronchospasm, laryngospasm, or angioedema
- Any indication of internal organ involvement (hepatitis, nephritis)

In the absence of the above signs or symptoms, subjects with Grade 2 allergic reaction may continue the study drug at the discretion of the Investigator. The subject should be advised to contact the Investigator immediately if there is any worsening of the allergic reaction and/or if any systemic signs or symptoms worsen. If the allergic reaction is considered to be most likely due to concomitant illness or non-study medication, standard management, including discontinuation of the likely causative agent, should be undertaken. If no other causative factor is found after clinical evaluation, the subject may be treated symptomatically until the rash resolves. Antihistamines, topical corticosteroids or antipruritic agents may be prescribed. The subject should remain on the study to be followed for safety and PK as outlined in the Time and Events table.

Grade 3 allergic reaction (Generalized urticaria or angioedema):

Subjects will permanently discontinue the study medication and be withdrawn from the trial. Subjects will be treated as clinically appropriate. Subjects should be followed up until resolution of the adverse event and standard management should be undertaken.

Grade 4 allergic reaction (Anaphylaxis):

Subjects will permanently discontinue the study medication and be withdrawn from the trial. Subjects will be treated as clinically appropriate. Subjects should be followed up until resolution of the adverse event and standard management should be undertaken.

Revised ACTG Toxicity Grade	Definitions	Investigator Action
Grade 1	Pruritus without rash	May continue therapy
Grade 2	Localized urticaria	May continue therapy
Grade 3	Generalized urticaria Angioedema	Discontinue Therapy
Grade 4	Anaphylaxis	Discontinue Therapy

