5.4. Withdrawal/Stopping Criteria

Subjects may voluntarily withdraw from the study at any time and for any reason. Site investigators and study staff may withdraw participants before their scheduled termination visit for safety, behavioral, or administrative reasons, or if the participants are unable or unwilling to comply with study procedures. The reasons for withdrawals will be recorded in the participants' study records. If a subject withdraws from the study, he/she may request destruction of any samples taken, and the investigator must document this in the site study records.

During the oral lead-in period, early withdrawal on medical grounds will occur if the participant develops a grade 3 or higher AE that is judged by the investigator to be related directly to the study product (see [Appendix 3](#) and [Appendix 4](#) for definitions and grading of severity of adverse events), or any AE that is deemed clinically significant by the investigator and is judged by the investigator to be related directly to the study product. For liver-related stopping criteria, please refer to [Section 5.4.1](#).

If a subject receives the IM injection of CAB LA, they will be followed 52-weeks post injection per protocol for appropriate procedures, including blood plasma PK sampling, and safety evaluations, and will not be removed from the study for medical reasons, unless they refuse to continue participation.

During the oral lead in phase additional pre-specified reasons for discontinuing a participant from the study (or, at minimum, discontinuing administration of study product and continuing safety evaluations) include:

- Pregnancy (please see [Section 7.4.2](#))
- Protocol deviation
- Non-compliance
- Subject withdraws consent
- Subject lost to follow-up
- Investigator discretion
- Sponsor discontinues study

The following actions must be taken in relation to a subject who fails to attend the clinic for a required study visit:

- The site must attempt to contact the subject and re-schedule the missed visit as soon as possible.
- The site must counsel the subject on the importance of maintaining the assigned visit schedule and ascertain whether or not the subject wishes to and/or should continue in the study.

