- In cases where the subject is deemed ‘lost to follow up’, the investigator or designee must make every effort to regain contact with the subject (where possible, 3 telephone calls and if necessary a certified letter to the subject’s last known mailing address or local equivalent methods). These contact attempts should be documented in the subject’s medical record.
- Should the subject continue to be unreachable, only then will he/she be considered to have withdrawn from the study with a primary reason of “Lost to Follow-up”.

For participants who have only received oral doses of CAB and develop an adverse effect which meets criteria for stopping the administration of study product, safety visits and follow-up will be continued until the resolution of the event, and then the subject will be withdrawn from the study and will not receive the CAB LA injection. If participants are unable to receive the IM injection for any reason, they will have a follow-up/withdrawal visit within 10-14 days of the last oral dose of CAB and then be terminated from the study. If the reason is HIV acquisition or pregnancy, refer to Section 7.4.1.6 and Section 7.4.2, respectively. For participants who develop an adverse effect which meets criteria for stopping the administration of study product, and have received both the oral CAB and an IM injection of CAB LA, follow-up and safety visits will be continued for a total of 52 weeks after the injection of CAB LA. All follow-up visits and scheduled safety evaluations (enumerated in the Time and Events Table in Section 7.1) will remain the same.

The medical monitor should be informed of all study withdrawals.

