5.4.1. Liver Chemistry Stopping Criteria

For subjects with ALT elevation $\geq 1.25x$ but $< 3xULN$, retest ALT within one week. If the retest ALT is $< 1.25x ULN$, subjects may continue to Day 28 dosing. If the retest ALT is $\geq 1.25x ULN$, dosing will be terminated, and subjects are prohibited from entering the injection phase. Weekly assessments should be conducted until ALT is $< 1.25x ULN$. For subjects with ALT elevation $\geq 1.25x ULN$ at Day 29, dosing will be terminated, subjects are prohibited from entering the injection phase, and weekly assessments should be conducted until ALT is $< 1.25x ULN$. Subjects with ALT $\geq 3xULN$ at any time point will be discontinued from study treatment. Please refer to the Liver Safety Required Actions and Follow up Assessments Section in [Appendix 2](#) for subsequent evaluations. If any of the above develops, please notify the medical monitor.

[figure not shown]
Standard liver chemistry stopping and increased monitoring criteria have been designed to assure subject safety and evaluate liver event etiology (in alignment with the

FDA premarketing clinical liver safety guidance).

<http://www.fda.gov/downloads/Drugs/GuidanceComplianceRegulatoryInformation/Guidances/UCM174090.pdf>

Study treatment will be discontinued **for a subject** if liver chemistry stopping criteria are met prior to CAB LA injection. If liver stopping criteria are met after receiving a CAB LA injection, subjects will not be withdrawn from the study but continue to have safety assessments performed as noted below and within the Time and Events table for 52 weeks post-injection or until resolution of the liver event, whichever is longer.

Liver Chemistry Stopping Criteria – Liver Stopping Event Algorithm

Liver Safety Required Actions and Follow up Assessments Section can be found in [Appendix 2](#).

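### Four toxicity rules in Appendix 5 order withdrawal from the trial with no limit to the pre-injection period, contradicting Section 5.4 for injected subjects

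*Protocol*

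**What the plan says.** **Section 5.4** ties withdrawal on medical grounds to the oral lead-in. Once CAB LA has been injected, the subject is followed for 52 weeks and "will not be removed from the study for medical reasons, unless they refuse to continue participation". For injected subjects whose adverse effect meets stopping criteria, the same section says that "follow-up and safety visits will be continued for a total of 52 weeks after the injection of CAB LA" and that the schedule of visits and safety evaluations does not change.

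**Section 5.4.1** (liver chemistry) writes the split out. If the criteria are met after injection, "subjects will not be withdrawn from the study but continue to have safety assessments performed as noted below", for 52 weeks or until the liver event resolves, whichever is longer.

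**Appendix 5** gives these instructions:

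- Grade 1 or 2 anemia: "If one or more of the additional tests is abnormal or suggestive of hemolytic anemia as specified above, subjects will permanently discontinue study medication"; the order in full is that "subjects will permanently discontinue study medication and be withdrawn from the trial".
- Grade 3 or 4 anemia, and Grade 3 or 4 total bilirubin: the same order, without any condition.
- Grade 3 and Grade 4 allergic reaction: "Subjects will permanently discontinue the study medication and be withdrawn from the trial".
- Follow-up is tied to the event. For bilirubin: "Subjects should be followed up until resolution (return to baseline) of bilirubin elevation".
- Rash at every grade, and Grade 1-2 allergic reaction: "The subject should remain on the study to be followed for safety and PK".

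**Sections 4.1.4 and 5.5** ask for best efforts to obtain the full 52 weeks of safety and PK assessments from an injected subject who is withdrawn or withdraws.

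**The concern.** A single long-acting dose cannot be taken back. Stopping rules that make sense for a daily tablet have a different effect once the injection is given: the subject stays exposed, and withdrawal removes only the observation. Section 5.4 recognises this. The four Appendix 5 rules do not. A site that follows the appendix literally would withdraw a subject with a significant toxicity, whose safety follow-up matters most.

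Two kinds of data are at stake: the rest of the 52-week safety follow-up, and the later concentrations in the primary endpoint (CWk8 and CWk12 in plasma, cervical and rectal tissue, and luminal fluids, and CWk8 in vaginal tissue).

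**Working it through.** The plan gives no figure to reproduce. The check compares the texts and then counts what is at risk.

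**1. Do the four rules carry a phase limit?** No. Each orders two acts, stopping the drug and leaving the trial, and none mentions the oral lead-in or the injection.

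**2. Can they be triggered after injection?** Yes. Section 7.1.2 schedules hematology and chemistry at Weeks 4, 8 and 12. Allergic reactions are not tied to a visit.

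**3. Does the protocol separate stopping drug from leaving the study elsewhere?** Yes, twice. In Appendix 5 itself, Grade 3 and Grade 4 rash stop the drug but keep the subject on study. Section 5.4.1 has an explicit post-injection exception. The four rules have neither.

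**4. Related rule.** Section 5.4.2 (QTc) also orders withdrawal without a phase limit. It has almost no reach after injection, because the Time and Events tables schedule no ECG after oral Day 14.

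**5. What is at risk per affected subject.** The primary tissue and fluid time points are C48h, Cd8, CWk4, CWk8 and CWk12 (5); for vaginal tissue they are C48h and CWk8 (2). Assume that samples due at the trigger visit are taken and that nothing later is.

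| Laboratory trigger | Tissue/fluid points lost | Vaginal tissue lost | Safety follow-up lost |
|---|---|---|---|
| Week 4 | 2 of 5 | 1 of 2 | 52 − 4 = 48 weeks (48/52 = 92%) |
| Week 8 | 1 of 5 | 0 of 2 | 52 − 8 = 44 weeks (44/52 = 85%) |
| Week 12 | 0 of 5 | 0 of 2 | 52 − 12 = 40 weeks (40/52 = 77%) |

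An allergic reaction before Day 3 would put all 5 tissue and fluid points at risk.

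**6. Effect on precision.** The target is 8 subjects per sex (Section 4.3). The half-width of a 95% CI for a mean on the log scale, in SD units, is t(0.975, n−1)/√n:

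- n = 8: 2.365/√8 = 0.836
- n = 7: 2.447/√7 = 0.925
- ratio: 0.925/0.836 = 1.106

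Losing one subject of one sex at CWk8 and CWk12 widens that group's interval by about 11%, if the SD is equal, all 8 would otherwise be sampled, and the subject is not replaced.

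**The case against.** The strongest reply is that Section 5.4 already decides the case. It deals with injected subjects who meet stopping criteria and keeps their visits unchanged, so Appendix 5 can be read as the list of triggers and Section 5.4 as the consequence in each phase. The appendix wording also fits the oral phase, since after one injection there is no medication left to stop. Even a subject withdrawn literally falls under Section 4.1.4, which covers injected subjects who are withdrawn and names PK. Follow-up until resolution is a duty and does not itself cancel the 52 weeks.

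This reading is plausible and is probably what was intended, but the text does not state it. The rash rules show that the appendix says so when it means a subject to stay on study, and Section 5.4.1 shows how the exception is written when it is meant. Section 4.1.4 replaces a firm rule with best effort, after the subject has been withdrawn.

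Two further points stand in part. First, Section 5.4 names safety visits and plasma PK, not tissue or fluid sampling, so aligning Appendix 5 with it would not by itself secure the biopsies; the fix has to name PK sampling. A subject with severe anemia might also reasonably skip biopsies under any wording. Second, the counts are upper bounds. Replacement is allowed at the sponsor's discretion (Section 4.3), the SAP keeps available data from withdrawn subjects (Section 5.5), and no hypothesis is tested.

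**Conclusion.** The contradiction is real and the text is wrong as written. For an injected subject with one of these four toxicities, Section 5.4 forbids medical removal and Appendix 5 orders it. The consequence is minor. Nothing in the primary analysis fails, and the figures above are maxima for a single affected subject if the site follows Appendix 5 and the recall efforts fail. The documents give no trigger rate; in healthy volunteers it is probably low. The main reason to act is the safety follow-up of a subject who has had a toxicity and still carries the drug. The possible loss of late tissue and fluid concentrations comes second.

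**What to change.** In the Appendix 5 rules for anemia (Grade 1-2 with an abnormal work-up, and Grade 3-4), Grade 3-4 bilirubin and Grade 3-4 allergic reaction, and in Section 5.4.2, limit withdrawal from the trial to the period before the CAB LA injection. For the period after it, adapt the Section 5.4.1 provision: the subject is not withdrawn and continues the Time and Events assessments, including plasma, tissue and fluid PK sampling where medically safe, for 52 weeks or until the event resolves, whichever is longer. The Appendix 5 rash rules already contain a usable model sentence.

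The cost is protocol wording only. No visit, procedure or analysis is added.

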12.6. Appendix 6: Collection of Pregnancy Information

- Investigator will collect pregnancy information on any female subject, who becomes pregnant while participating in this study
- Information will be recorded on the appropriate form and submitted to GSK within 2 weeks of learning of a subject's pregnancy.
- Subject will be followed to determine the outcome of the pregnancy. The investigator will collect follow up information on mother and infant, which will be forwarded to GSK. Generally, follow-up will not be required for longer than 6 to 8 weeks beyond the estimated delivery date.
- Any termination of pregnancy will be reported, regardless of fetal status (presence or absence of anomalies) or indication for procedure.
- While pregnancy itself is not considered to be an AE or SAE, any pregnancy complication or elective termination of a pregnancy will be reported as an AE or SAE.
- A spontaneous abortion is always considered to be an SAE and will be reported as such.
- Any SAE occurring as a result of a post-study pregnancy which is considered reasonably related to the study treatment by the investigator, will be reported to GSK as described in [Appendix 3](#). While the investigator is not obligated to actively seek this information in former study participants, he or she may learn of an SAE through spontaneous reporting.

Any female subject who becomes pregnant while participating

- Oral Phase: Will cease to have any drug administered, but will continue to receive safety, clinical and laboratory monitoring to minimize further exposure to the fetus.
- Injection Phase: will continue to receive safety, clinical and laboratory monitoring through the completion of the pregnancy.

12.7. Appendix 7: Schedule for Additional Laboratory Procedures for Enrolled Participants who have a Reactive Positive HIV Test Result (Post-HIV Confirmation Visit)

Post-HIV Confirmation Visit	
Refer for care	X
HIV Counseling	X
Offer Condoms	X
Clinical Evaluations and Procedures	
Blood collections for plasma storage ¹	X
Schedule Follow-up Visits ²	X
CD4 Cell Count ³	X
HIV Viral Load ³	X
HIV Resistance Testing ³	X

(1) Stored plasma samples will be collected from participants who acquire HIV infection, these assessments may include PK assessment, resistance testing, HIV subtyping, characterization of the virus and/or the host response to infection. These assessments will be performed retrospectively; results will not be returned to study sites or participants.

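### Appendix 5 and Section 5.4.2 order withdrawal from the trial with no phase limit, while Section 5.4 forbids removing an injected subject for medical reasons

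*Protocol*

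**What the plan says.** **Withdrawal with no phase stated.** Protocol Section 12.5 (Appendix 5) covers Grade 3 allergic reaction (generalized urticaria or angioedema) and Grade 4 (anaphylaxis) with the same instruction: "Subjects will permanently discontinue the study medication and be withdrawn from the trial". It then adds: "Subjects should be followed up until resolution of the adverse event and standard management should be undertaken". Neither entry, nor the summary table below them, names a study phase or requires the event to be drug-related.

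The same kind of instruction appears in three other places:

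- Anemia (Appendix 5): always at Grades 3-4, and at Grades 1-2 when one of the additional tests is abnormal or suggests hemolysis.
- Total bilirubin (Appendix 5): Grades 3-4.
- QTc (Section 5.4.2): above 500 msec, or a rise from baseline above 60 msec.

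**No removal after injection.** Section 5.4 places medical withdrawal in the oral lead-in. A subject who has had the injection is to be followed for 52 weeks and "will not be removed from the study for medical reasons, unless they refuse to continue participation". If such a subject has an adverse effect that meets stopping criteria, "follow-up and safety visits will be continued for a total of 52 weeks after the injection of CAB LA".

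**Places where the protocol is explicit.** For liver events, Section 5.4.1 says: "If liver stopping criteria are met after receiving a CAB LA injection, subjects will not be withdrawn from the study". For pregnancy, Appendix 6 says: "Injection Phase: will continue to receive safety, clinical and laboratory monitoring through the completion of the pregnancy". For Grade 3 rash, Appendix 5 says: "The subject should remain on the study to be followed for safety and PK as outlined in the Time and Events table". Grade 4 rash carries almost the same sentence.

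**The concern.** Take an injected subject who develops angioedema. Appendix 5 says the subject will be withdrawn, and Section 5.4 says the subject will not be removed. Both are mandatory, and no precedence clause appears in the text available. Two sites could handle the same event in opposite ways, each citing the protocol.

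What turns on it is first the subject's status. Under Section 5.5, withdrawal before PK assessments through Week 12 are complete makes the subject a non-completer for treatment and study. Under Section 4.3 that subject may be replaced. Under Section 5.4 the same subject stays in, with the remaining primary timepoints still scheduled.

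The second stake is follow-up. For a retained subject it is part of the study. For a withdrawn one, Section 4.1.4 asks only for every effort to bring the subject back. Section 4.6.1 itself warns that long exposure after the injection may complicate management of a hypersensitivity reaction, so this is a poor subject in whom to weaken the obligation.

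**Working it through.** The plan has no figure of its own to reproduce here; Section 9.2.1 reports no formal sample size calculation. The check is mainly a comparison of texts, followed by a sizing of the consequence.

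**1. The two rules for an injected subject with a Grade 3-4 allergic reaction**

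| Question | Appendix 5 | Section 5.4 |
|---|---|---|
| Trial status | Withdrawn | Not removed unless the subject refuses |
| Follow-up | Until the event resolves | 52 weeks after injection |
| Phase | Not stated | Post-injection, explicitly |

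The status row cannot be reconciled. The follow-up row can: following an event to resolution does not by itself cancel later visits.

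**2. Does the wording imply the lead-in only?** CAB LA is given once (Section 6.1), so nothing is left to discontinue after injection. However, Appendix 5 also tells Grade 3-4 rash subjects to discontinue study medication permanently, and then keeps them on study. The phrase therefore does not decide trial status. Read literally, an injected subject with Stevens-Johnson syndrome stays and one with generalized urticaria leaves.

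**3. Where a trigger could arise after injection.** Hematology and chemistry are scheduled at Weeks 4, 8 and 12 (Section 7.1.2), so anemia and bilirubin triggers can appear at routine visits. No ECG is scheduled after injection, so a QTc trigger would need an unscheduled one.

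**4. Samples exposed.** Assume a reaction on Day 8 after that day's samples, exit before Week 4, and no return under Section 4.1.4.

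- Compartmental timepoints are Day 3, Day 8 and Weeks 4, 8 and 12, which makes 5. Weeks 4, 8 and 12 are lost: 3 of 5.
- Post-dose plasma samples are 4 h, Days 3, 5 and 8, and Weeks 4, 8, 12, 24, 36 and 52, which makes 10. The last 6 are lost: 6 of 10.
- HIV tests are scheduled at Weeks 12, 24, 36 and 52: all 4 scheduled tests are lost.
- Against this, the Withdrawal visit in Section 7.1.2 supplies one plasma PK sample and one HIV test.

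**5. Drug still present.** Section 2.2 gives a half-life of about 21-50 days. Assume first-order decline and 7-28 days to resolution; neither assumption comes from the documents. The fraction remaining is 0.5^(t/half-life):

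- 7 days: 0.5^(7/21) = 0.794 to 0.5^(7/50) = 0.908
- 28 days: 0.5^(28/21) = 0.397 to 0.5^(28/50) = 0.678

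So roughly 40% to 91% of the concentration remains.

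**6. Precision, worst case.** The 95% CI half-width in SD units is t(0.975, n-1)/sqrt(n).

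- n = 8: 2.365/2.828 = 0.836
- n = 7: 2.447/2.646 = 0.925
- Ratio: 0.925/0.836 = 1.106, about 11% wider

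**7. Frequency.** Section 4.6.1 reports no clinical cases of CAB hypersensitivity, and Section 2.2 gives about 566 people injected. The one-sided 95% upper limit for 0/566 is 1 - 0.05^(1/566) = 0.00528, or 0.53%. In 16 subjects that is at most 16 x 0.00528 = 0.084 expected. This bound covers CAB hypersensitivity only. The documents give no rate for allergic reactions from other causes, or for the anemia, bilirubin and QTc triggers.

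**The case against.** The best defence is that the protocol, read as a whole, already answers the question. Section 5.4 is the specific post-injection rule. Missing phase wording recurs in the anemia, bilirubin and QTc criteria, which suggests a drafting habit with Section 5.4 supplying the general split. On follow-up, Section 5.4 keeps all visits and scheduled safety evaluations unchanged for an injected subject who meets stopping criteria. Sections 4.1.4 and 5.5 seek the same 52 weeks even after withdrawal.

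Much of this stands. A reader might infer that follow-up would simply end when the reaction resolves. The documents do not support that: no passage says scheduled visits stop then, and following to resolution can be read as ordinary adverse-event follow-up, as in Section 7.4.1.4.

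A reader might also infer an 11% loss of precision. That would apply only at Weeks 4 to 12 and only without replacement. Section 4.3 permits replacement, about 20 are enrolled to obtain 16, and SAP Section 5.5 summarizes available data from withdrawn subjects according to the analysis populations. A subject with Day 3 and Day 8 data can still count as evaluable.

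What does not stand is the claim that nothing conflicts. Harmonizing the texts requires a phase limit that Appendix 5 and Section 5.4.2 do not contain. The recurrence of the omission widens the problem rather than explaining it away.

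**Conclusion.** Wrong as written: an internal contradiction of minor severity. After injection, Appendix 5 and Section 5.4.2 order withdrawal for events for which Section 5.4 forbids removal. The main consequence is inconsistent trial status. The secondary one is that required follow-up, and the compartmental samples still due by Week 12, could become best effort.

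The sample counts rest on an assumed Day 8 event, a site following Appendix 5 over Section 5.4, and failure of the return sought by Section 4.1.4. The 11% is a ceiling for one loss from a group of 8 without replacement. For CAB hypersensitivity the expected count is at most about 0.08 in 16; the other triggers cannot be sized from the documents.

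A reader might also infer a conflict during the lead-in. There is none. Section 4.6.1 already stops oral CAB on suspected hypersensitivity, and Section 5.4 already bars the injection once stopping criteria are met.

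**What to change.** Add one sentence at the head of Appendix 5 and again in Section 5.4.2:

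*Withdrawal from the trial under these criteria applies only before the CAB LA injection; after the injection the subject is not withdrawn and continues safety and plasma PK assessments under Section 5.4 to Week 52 or until resolution of the event, whichever is longer.*

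Placing it at the head of the appendix matters. A carve-out for allergic reactions alone could imply that the anemia and bilirubin withdrawals do apply after injection. The wording follows the model of the liver rule in Section 5.4.1. No lead-in sentence is needed.

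The cost is one sentence in two places, by amendment or clarification letter. It adds no threshold, scheduled visit or test, because Section 7.1.2 already runs to Week 52 and Appendix 5 already follows these events to resolution. For QTc, explicit follow-up to resolution would be new wording in Section 5.4.2.
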